Primary outcomes	
Primary outcomes assessed at T2 (change from baseline):
 
(i) Exercise mindset using the Mindset about the Process of Health – Exercise scale. This one-factor scale was developed and validated¹ to assess mindset about the process of engaging in physical activity (e.g., physical activity is difficult/easy, unpleasant/pleasurable, boring/fun). The scale consists of 7 items and is measured on a 4-point scale and scored from 1 to 4, with a higher score reflecting a more appeal-focused mindset about exercise
 
(ii) Osteoarthritis mindsets using the Illness Mindset Inventory. The Illness Mindset Inventory measures three mindsets about the nature and meaning of illness: that it is a catastrophe, manageable, or an opportunity. The scale consists of 20 items measured on a 6-point scale and scored from 1 to 6, with 10 of those questions capturing mindsets about chronic illness. The extent to which a participant endorsed each mindset was obtained by calculating the respective mean scores. A higher score indicates greater agreement with the mindset. This Illness Mindset Inventory is valid and reliable in individuals with knee osteoarthritis². We adapted the scale to focus on mindsets about "knee osteoarthritis" as opposed to "chronic disease."
 
Primary outcomes assessed at T3 (change from baseline):
 
(i) Knee pain using the question, "What was your average osteoarthritis-related pain over the past week?" and measured on an 11-point Numeric Rating Scale (NRS) from 0 (no pain at all) to 10 (the worst pain imaginable)
 
(ii) Physical activity using the Physical Activity Scale for the Elderly (PASE). The PASE asks respondents about the frequency of light, moderate, and strenuous work and leisure activities and is a validated measure of self-reported physical activity for individuals with osteoarthritis³. The scale is scored from 0 to 793 with higher scores indicating higher levels of physical activity.

Secondary Objectives	
Key secondary	Secondary outcomes assessed at T2 (change from baseline):

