We will randomize 505 individuals aged ≥ 45 years with knee osteoarthritis into one of three groups with 1:1:1 group allocation: the Mindset Group (participants receive a digital mindset intervention to improve mindsets about osteoarthritis and exercise), the Education Group (Participants receive a series of osteoarthritis education videos and reflective questions that matches the digital mindset intervention in duration and attention), or the No-Intervention Group (participants take the same surveys as the other groups at the same time points, but do not receive any additional content). Participants will complete an initial baseline survey and be randomized one week later. Those randomized to the Mindset and Education Groups will have one week to complete the self-paced online programs. All groups complete osteoarthritis knowledge and mindset surveys at this timepoint. One-month later, participants will receive a follow-up questionnaire.

Study Setting

The study will be conducted entirely online.

Eligibility Criteria

Inclusion Criteria:

- Over 45 years of age
- Self-reported doctor's diagnosis of knee osteoarthritis OR meets the National Institute for Health and Care Excellence osteoarthritis clinical criteria (activity-related knee pain and no knee morning stiffness lasting ≥ 30 minutes)
- Knee pain for at least 3 months
- Ability to walk unaided
- Can read and write in English
- Consistent internet access
- Willingness and ability to comply with the study requirements

Exclusion criteria:

- Past total knee arthroplasty or scheduled surgical procedure on any back or

- lower limb with osteoarthritis within the next 12 months
- Recent serious injury (within the past 2 months) on the knee(s) with osteoarthritis
- Any condition making it unsafe to participate in physical activity
- Intra-articular therapy within the past 6 months (e.g. injections such as corticosteroids and hyaluronic acid)
- Participates in physical exercise for 30 minutes or more 5 days per week

Interventions

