Intervention(s)	
Mindset Group: Participants receive a digital mindset intervention to improve mindsets about osteoarthritis and exercise.
 
Education Group (active comparison): Participants receive a series of osteoarthritis education videos and reflective questions that matches the digital mindset intervention in duration and attention.
 
No-Intervention (control): Participants take the same surveys as the other groups at the same time points, but do not receive any additional content.

-----------------	--

Modifications

Discontinuation of the program due to psychological disturbance. We do not expect participants to have a psychological disturbance due to the mindset intervention or active comparator program. In the case that someone refuses to continue the study due to a psychological disturbance from participation, this should be reported as an adverse event.

Adherence

[figure not shown]
Adherence reminders will be in the form of emails. Three reminders will be sent out: once before the deadline, on the deadline, and the day after the deadline. Reminders will include the importance of completing the section in order to remain in the study. Reminders will also include a flow chart of the study timeline and components, with the relevant section highlighted. Participants will be able reply to the study coordinator with questions.

Concomitant Care

Participation is at the discretion of the participants. Thus, the other option for participants is to not participate in the study.

Prohibited Concomitant Treatment. Additional physical therapy treatment is not permitted during the study as it would interfere with the main outcomes of our study.

Study Flow and Timeline

Supplement 1 Figure 1. Study flow and timeline.

Sample Size

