$$P_{\Delta} \left(\frac{T}{\sqrt{2\sigma^2/n}} > z_{1-\alpha} \right) \geq 1 - \beta$$

which is equivalent to

$$n \geq \frac{2\sigma^2(z_{1-\alpha} + z_{1-\beta})^2}{\Delta^2}$$

[figure not shown]
For our analysis, we choose $\alpha = 0.05$, and try four different values of β , 0.05, 0.10, 0.15, and 0.20. We estimate σ from pilot data.

Outcome variable, PASE

[figure not shown]
[figure not shown]

sigma = 70.27939

A priori sample size analysis for outcome variable, PASE

[figure not shown]

Pain Scores

sigma = 1.670426

A priori sample size analysis for outcome variable, pain

Recruitment

Participants will be recruited through paid online and social media advertising and local flyer postings.

Allocation

We will use the randomizer function in Qualtrics to randomize participants into one of three groups (1:1:1): the Mindset Group, the Education Group (active comparison), or the No-Intervention Group (control).

Blinding (Masking)

During the informed consent process, participants will be informed that the purpose of the study is to understand the effect of a new online osteoarthritis program and that they will be randomized to either a no-intervention group or one of two different sets of videos and reflective questions. Participants will be aware of whether they are randomized to an online program; however, the differences in content between the two programs and the hypotheses of the study will not be revealed. The biostatistician performing the data analysis will be blinded to the group labels.

Data Collection, Management, and Access

All data will be collected through the Qualtrics online survey software. Qualtrics encrypts all transmitted data using Transport Layer Security and hosts data on data centers that are independently audited using the industry standard SSAE-18 method. Stanford University has a Qualtrics license for research use, and data obtained from the Qualtrics platform can only be accessed through a secure login. Data will be exported to Microsoft Excel and securely stored for use by the research team. Only after de-identification may the data be shared outside of the research team.

Missing Data

Participants who did not complete a survey entirely were removed from the study and not sent the follow-up survey. Each question of each survey was “force response,” meaning that if a participant completed the survey, no answers would be missing from the response. Thus, no methods for missing data were implemented.

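### Randomised participants who miss the post-intervention survey are removed and never sent the one-month survey, so with no missing-data method the four Bonferroni-corrected comparisons of pain and PASE are made among completers

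*Combined protocol and SAP*

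**What the plan says.** The Missing Data section sets the rule: "Participants who did not complete a survey entirely were removed from the study and not sent the follow-up survey". It adds that every question required a response, and concludes: "Thus, no methods for missing data were implemented".

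The Trial Design section gives the order of events. On randomisation: "Participants will complete an initial baseline survey and be randomized one week later". After the one-week programme period: "All groups complete osteoarthritis knowledge and mindset surveys at this timepoint". Then: "One-month later, participants will receive a follow-up questionnaire".

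The Study Objectives table places NRS pain and PASE under the heading "Primary outcomes assessed at T3 (change from baseline"). Statistical Methods compares changes by pooled-variance t-test, with a Bonferroni threshold of 0.0125 for four comparisons: Mindset v Education and Mindset v No-Intervention, each for pain and physical activity at one month.

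On attrition, Sample Size anticipates 20% dropout and inflates enrolment to 501. The Adherence section provides email reminders ("Three reminders will be sent out: once before the deadline, on the deadline, and the day after the deadline") which stress that completion is needed to stay in the study. Data Monitoring includes retention among the topics reviewed. Statistical Methods promises a baseline comparison of completers with dropouts. No section defines an analysis set, an imputation or likelihood-based method, or a sensitivity analysis.

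**The concern.** Removing someone who fails to finish the baseline survey is harmless, because that happens before randomisation. Removing someone who fails to finish the post-intervention survey is a post-randomisation exclusion: the person has been allocated, may be willing to answer at one month, and is not asked.

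Forced response does not justify this. It guarantees that a submitted survey has no blank items, but it does nothing about surveys never submitted, and the plan itself expects a fifth of participants to be lost.

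At stake is whether the pain and PASE comparisons estimate an effect in the people randomised or a difference between those who stayed in each arm. The two can differ if dropout, or the kind of person who drops out, differs by arm. That is most plausible for Mindset v No-Intervention, where one arm has a week-long programme before the post-intervention survey and the other has surveys only. Sample Size counts improvement in either pain or PASE as success, so a shift in PASE alone could matter.

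**Working it through.** **Step 1. Which survey triggers the exclusion.** The Missing Data section does not name the survey, and the surviving text does not define T1 to T3. In the Trial Design sequence (baseline, randomisation, post-intervention survey, one-month questionnaire) only the post-intervention survey lies between randomisation and follow-up. Identifying it as T2 is an inference, well supported by the outcome timings in the Study Objectives table and Statistical Methods.

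**Step 2. Whether the exclusion is needed.** Change in pain and PASE runs from baseline to one month. No post-intervention data enter it, so missing that survey does not prevent the outcome from being computed. Only the removal rule does.

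**Step 3. The plan's own figures.** From Sample Size and its appendix: SD 70.28 (PASE) and 1.67 (pain), target 26 PASE points, 80% power.

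- n = 2 × 70.28² × (2.241 + 0.842)² / 26² = 138.9, so 139 per group, as stated. This uses one-sided 0.0125.
- 417 × 1.2 = 500.4, so 501, as stated.
- 20% of 501 is about 100 people without a one-month change score. 167 × 0.8 = 133.6 per arm remain; 133 is used below.

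The inflation protects power. It does not address selection.

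**Step 4. Illustrative size.** Arm-level dropout (p) and the gap (k, the number of SDs by which dropouts would have changed less favourably than completers) are assumptions; the documents give only 20% overall. Dropout here is *all* loss: removal at the post-intervention survey plus non-response at one month. The t-test's sidedness is not stated, so two-sided values lead.

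Bias in SD units = p₁k₁ − p₂k₂. SE = √(1/133 + 1/133) = 0.1226. Type I error = P(|Z + bias/SE| > 2.498).

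| Scenario | Bias (SD) | PASE | NRS | Two-sided type I error (nominal 1.25%) |
|---|---|---|---|---|
| Mindset v No-Intervention, 25% v 15%, k = 0.25 | 0.025 | 1.8 | 0.04 | 1.4% |
| Mindset v No-Intervention, 25% v 10%, k = 0.5 | 0.075 | 5.3 | 0.13 | 3.1% |
| Either comparison, equal dropout and equal gaps | 0 | 0 | 0 | 1.25% |
| Mindset v Education, 20% in each, k = 0.5 v 0.25 | 0.05 | 3.5 | 0.08 | 2.0% |

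In the second row, 0.075 × 70.28 = 5.27, which is 20% of 26, and 0.075 × 1.67 = 0.125. Dropout of 25%, 25% and 10% across the three arms averages the planned 20%. One-sided, the first two rows give 2.1% and 5.2%.

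**Step 5. Direction.** In the first two rows dropouts do worse and Mindset loses more people, so the bias favours Mindset. In the second row, two-sided power for 26 PASE points would rise from 70% to about 87%. A loss of power would need the gap or the dropout imbalance reversed. The 70% itself reflects the two-sided threshold and the number retained, not this defect.

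**Step 6. Share due to the removal rule.** Take the second row and suppose half of each arm's dropout is removal at the post-intervention survey, with everyone so removed answering at one month if asked. Sending the survey then removes 70.28 × k_T2 × (0.125/0.875 − 0.05/0.95) PASE points, where k_T2 is the gap for those removed. With k_T2 = 0.25, 0.5 or 0.75 (and 0.75, 0.5 or 0.25 for one-month non-responders, keeping the total at 5.3) this is 1.6, 3.2 or 4.8 points. The documents supply neither the split nor the gaps, so this share cannot be identified.

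**The case against.** The strongest reply has four parts.

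*The size is conjecture.* This stands. Every figure in Step 4 rests on assumed arm-level dropout and gaps. The mild case barely moves type I error, and the pain shift is 0.13 points against the plan's 2-point difference. A reader might infer that the PASE result will be inflated by about five points, that power will be lost, or that the removal rule accounts for the whole bias. The documents support none of these: they fix neither direction nor size, and some of the loss is ordinary one-month non-response.

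*The Education comparison is protected.* Largely so. The Education programme "matches the digital mindset intervention in duration and attention", which makes equal dropout and equal gaps plausible, and then the bias is zero. It reappears only if programme content changes who leaves or how many leave.

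*The plan already handles attrition.* Reminders and retention review may reduce loss, and the completer v dropout table describes it. None of them restores the randomised comparison.

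*It may be too late.* The Missing Data section is in the past tense, and Trial Design gives 505 to be randomised where the metadata table and Sample Size give 501. This suggests, without proving, that collection was under way or finished when the text was written. If it has closed, the excluded outcomes cannot be recovered, which limits the remedy but leaves the analysis undefined.

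A reader might also conclude that the t-test on change must give way to a baseline-adjusted model. That is a separate improvement which this defect does not require.

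**Conclusion.** The point holds. A stated rule creates an avoidable exclusion after randomisation, the reason given for having no missing-data method does not cover missing surveys, and nothing elsewhere in the plan defines who is analysed or tests the effect of loss. The four corrected comparisons are therefore made among completers; this is implied by the use of change scores rather than stated. The mindset outcomes at T2, also labelled primary, are likewise limited to those who answered, but for them the post-intervention survey is the outcome itself.

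Under the assumptions shown, bias in Mindset v No-Intervention ranges from 1.8 to 5.3 PASE points in Mindset's favour, and it is zero when dropout and gaps are equal. These figures illustrate what the plan leaves open; they do not estimate what happened. The case for acting rests less on them than on the fact that the rule stops collection of the outcomes that would show whether bias exists. The conclusion depends on reading the intermediate survey as T2.

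**What to change.** 1. **If follow-up is still open**, replace the removal rule for randomised participants with: *All randomised participants will be sent the one-month survey, whether or not they completed the post-intervention survey or the programme.* Align the reminder wording in the Adherence section and document the change as a protocol amendment.
2. **Define the primary analysis set** as all randomised participants, as randomised, with a stated missing-data method: multiple imputation, or a likelihood-based model that includes baseline.
3. **Report attrition by arm and by survey**, and pre-specify a delta-adjusted missing-not-at-random analysis varied separately by arm, reporting where the conclusion changes. A range of 0 to 0.5 SD less favourable (0 to 35 PASE points, 0 to 0.84 NRS points) is one possibility; the team should fix the range.

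If collection has closed, step 1 is unavailable. People removed at the post-intervention survey then have no pain or PASE value after baseline, so step 2 adds little beyond a baseline-adjusted complete-case analysis. Step 3 carries the weight, and the results should be described as a completers analysis.

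Cost: an amendment, follow-up emails to up to about 100 people, SAP wording and extra analysis code. The estimated effect may be smaller than among completers.

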
outcomes
	
(i) Knee osteoarthritis knowledge by the Knee Osteoarthritis Knowledge Scale⁴. The Knee Osteoarthritis Knowledge Scale is scored from 11-55 and measures knowledge about osteoarthritis in individuals with knee or hip osteoarthritis
 
(ii) Body mindsets using the Illness Mindset Inventory. In addition to mindsets about chronic illness, the Illness Mindset Inventory measures three mindsets about the nature of the body in the context of a chronic illness: that it is adversarial, responsive, or resilient
 
(iii) Activity adequacy mindsets using the Adequacy of Activity Mindset Measure⁵. This scale was developed to assess mindsets about the adequacy and benefits of one's physical activity as it relates to health. The scale consists of 5 items measured on a 7-point scale and scored from 1 to 7, with a higher score reflecting a more adaptive mindset about the benefits and risks associated with current levels of physical activity.
 
Secondary outcomes assessed at T3 (change from baseline):
 
(i) Knee pain and functioning using the Short version of the Western Ontario and McMaster Universities Arthritis Index (shortMAC). The shortMAC is a disease-specific 12-item measure of knee symptoms and has shown to be valid and reliable in patients with knee osteoarthritis⁶. We evaluated the measure divided into two subscales: pain and function
 
(ii) Perceived need for surgery using the single question, "How likely do you think you are of needing knee replacement surgery in the future?" It was answered on the Likert scale from 1 (very unlikely) to 5 (very likely)
 
(iii) Chosen symptom management strategies using the single question, "Which of the following are ways in which you manage and/or improve your osteoarthritis symptoms? Please select all that apply." It was answered via multiple choice with a multiple-selection option. The options available were the most commonly identified responses as determined by a previous study⁷
 
(iv) Fear of movement using the Brief Fear of Movement Scale for Osteoarthritis⁸. The Brief Fear of Movement Scale for Osteoarthritis is a 6-item scale validated to assess fear of movement in individuals with osteoarthritis
 
(v) Arthritis self-efficacy using the Arthritis-Self Efficacy Scale. This scale is scored from 1 to 10, with higher scores indicating greater self-efficacy, and was divided into the "pain" and "other symptoms" subscales
 
(vi) Physical and Mental Health using the PROMIS v.1.1 Global Health Short Form⁹. This scale is a 10-item survey that measures overall physical function, fatigue, pain, emotional distress, and

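### Read literally, the removal rule for unfinished surveys also keeps pain and PASE answers given at one month out of the primary t-tests when the participant stops at a later secondary item

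*Combined protocol and SAP*

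**What the plan says.** The Missing Data section sets three rules.

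- Removal: "Participants who did not complete a survey entirely were removed from the study and not sent the follow-up survey".
- Compulsory items: every question of every survey requires a response, "meaning that if a participant completed the survey, no answers would be missing from the response".
- The inference drawn: "Thus, no methods for missing data were implemented".

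The Adherence section is in the same spirit: "Reminders will include the importance of completing the section in order to remain in the study".

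Trial Design describes the one-month contact as a single questionnaire. Supplement 1 Table 2 assigns it two primary outcomes, the knee pain NRS and PASE, and six secondary measures. These are the shortMAC ("The shortMAC is a disease-specific 12-item measure of knee symptoms"), one question on perceived need for surgery, one on symptom management, a 6-item fear of movement scale, a self-efficacy scale of unstated length, and PROMIS Global Health ("This scale is a 10-item survey that measures overall physical function").

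The plan defines no analysis set, no rule for partial responses and no option to decline an item. Statistical Methods adds only a baseline comparison of completers and dropouts, which recovers no outcome data.

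**The concern.** The rule treats a survey as all or nothing. At T3 this ties the primary outcomes to secondary items that the primary t-tests do not need. A participant may report pain and PASE and then stop at, or refuse, a question in a later scale. Both primary outcomes have then been observed, yet the plan gives that record no way into the primary comparison.

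Two things are at stake. One is avoidable loss of power for PASE. The other is selection after randomisation: whoever stays in the analysis has been filtered by willingness to finish the survey. Participants know whether they were given a program (Blinding), so that willingness could differ between arms.

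This is separate from the participant who leaves the post-intervention survey (T2) unfinished and is never sent T3. There the primary outcomes are never collected. Sending T3 to everyone, or imputing, would help that case but would not by itself keep answers already given in an unfinished T3 survey.

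**Working it through.** **Secondary items at T3** (Supplement 1 Table 2): 12 (shortMAC) + 1 (surgery) + 1 (symptom management) + 6 (fear of movement) + 10 (PROMIS) = 30, plus the self-efficacy scale.

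**Inputs for power** (Sample Size, the a priori power analysis and Statistical Methods): PASE difference 26; SD 70.27939; pain difference 2; SD 1.670426; threshold 0.0125; 501 enrolled, allocated 1:1:1; 20% dropout. The power derivation is one-sided. Statistical Methods does not state the sidedness of the test, so both are shown.

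**The plan's own figure.** n = 2σ²(z₁₋α + z₁₋β)²/Δ² = 2 × 70.27939² × (2.2414 + 0.8416)² / 26² = 138.9, so 139 per group at one-sided 0.0125 and 80% power. Then 3 × 139 = 417 and 417 × 1.2 ≈ 501 (rounded up). The plan's figures are reproduced.

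**The base for the loss.** 501/3 = 167 per arm. With 20% lost, 167 × 0.8 = 133.6 remain and 33.4 are lost. Someone who breaks off at T3 is a dropout under the plan's rule, so belongs among the 33.4 and is not an extra loss taken off 139.

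**PASE power from keeping partial responders.** Let f be the share of those lost who had answered PASE before stopping. The documents do not give f; 5% to 50% is assumed. Then n = 167 × (0.8 + 0.2f). Power is from the noncentral t for two equal groups, with d = 26/70.27939 = 0.370.

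| f | n per arm | Power, one-sided 0.0125 | Power, two-sided 0.0125 |
|---|---|---|---|
| 0 (none kept) | 133.6 | 77.9% | 69.4% |
| 5% | 135.3 | 78.4% | 70.1% |
| 50% | 150.3 | 82.9% | 75.6% |

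The gain runs from about half a percentage point to about 5 one-sided, or from under 1 to about 6 two-sided.

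**Pain.** d = 2/1.670426 = 1.20. Power at 133.6 per arm exceeds 99.9%, one- or two-sided, and retention can only raise it.

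**The case against.** The strongest reply is that the documents never say that partial T3 records are deleted. The removal sentence goes on to say that the person is not sent the follow-up survey. That fits baseline and T2, because T3 is the last survey. A reader might infer that the plan expressly throws away one-month answers; it does not. What remains is that the sentence speaks of a survey without excepting T3, and the claim that no missing-data method is needed holds for the primary analysis only if unfinished T3 records stay out of it.

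Second, the item order is not given. If pain and PASE come after the item at which someone stops, nothing has been observed and an analysis rule alone recovers nothing. This stands, and it is why the fix includes placement.

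Third, a reader might take 5%, 10% or 15% off the 139 per group and report the resulting fall in power. The documents do not support that: 139 is the number meant to remain after dropout, and no break-off rate is given.

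Fourth, all arms take the same surveys at the same times, so the T3 burden is equal by design. A difference between arms in finishing T3 is therefore a possibility, not something the documents show.

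Finally, compulsory items have a benefit: every finished survey yields complete scale scores. Dropping them is a trade-off. That does not defend excluding primary answers already in hand.

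**Conclusion.** The concern holds in limited form. Followed as written, the rule leaves a T3 survey that breaks off after pain and PASE with no route into the primary t-tests. This is a consequence of the rule's wording, not an explicit instruction, and it matters only where the primary items come before the stopping point.

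For PASE the cost is small to moderate and cannot be fixed from the documents. The range in the table rests on three assumptions: exactly the planned 20% is lost, loss is equal across arms, and 5% to 50% of those lost had answered PASE. For pain, power is not at issue. The only concern is possible selection after randomisation, whose size and direction are unknown. The change is worth making because it is cheap and protects observed primary data, not because a large loss has been shown.

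**What to change.** 1. Place the pain NRS and PASE at the start of the T3 questionnaire.
2. Set the survey software to save partial submissions.
3. Replace the removal rule with: *Each outcome is analysed in all randomised participants who answered it, whether or not the rest of the survey was finished.*

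The cost is survey settings and one sentence in the SAP. If T3 data have already been collected, the sentence can still be applied to any partial records that were saved.

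Optionally, secondary items could be made skippable. This trades complete scale scores for retention and needs a scoring rule for item gaps, so the investigators may reasonably decline it.

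These changes do not recover participants who were never sent T3 after an unfinished T2 survey. That needs its own provision.
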